Protocol for non-interventional studies based on existing data

Document Number:	c25002535-01
BI Study Number:	0205-0537
BI Investigational Product(s):	Spiriva Respimat
Title:	Characteristics of patients initiating Spiriva Respimat in Asthma in the UK: a cross-sectional study based on the Clinical Practice Research Datalink
Brief Lay Title	Characteristics of patients who start to use the Spiriva Respimat® to treat their Asthma: a study based on the Clinical Practice Research Datalink in the UK
Protocol version identifier:	1.1
Date of last version of protocol:	Not applicable
PASS:	No
EU PAS register number:	Not applicable
Active substance:	Tiotropium bromide (ATC code R03B B04)
Medicinal product:	Tiotropium® Respimat®
Product reference:	Not applicable
Procedure number:	Not applicable
Joint PASS:	No
Research question and objectives:	
The main objective of the study is to describe the clinical and socio-demographic characteristics of asthma patients prior to the initiation of Spiriva Respimat for the treatment of Asthma within a general clinical population using the Clinical Practice Research Database (CPRD).
 
A secondary objective will be to describe and compare the characteristics of asthma patients who initiated Spiriva Respimat to asthma patients who initiated a higher dose of ICS/LABA FDC, or leukotriene receptor antagonist (LTRA), or alternatively those who switched from the previous ICS/LABA FDC to a new ICS/LABA FDC.

Country(-ies) of study:	United Kingdom

Protocol for non-interventional studies based on existing data

BI Study Number 0205-0537

c25002535-01

Proprietary confidential information © 2018 Boehringer Ingelheim International GmbH or one or more of its affiliated companies

Author:	Tel.: Fax: E-mail:
Marketing authorisation holder(s):	
MAH contact person:	Not applicable
In case of PASS, add: <EU-QPPV:>	Not applicable
In case of PASS, add: <Signature of EU-QPPV:>	Not applicable
Date:	Aug 3, 2018
Page 1 of 47	
Proprietary confidential information © 2018 Boehringer Ingelheim International GmbH or one or more of its affiliated companies. All rights reserved. This document may not - in full or in part - be passed on, reproduced, published or otherwise used without prior written permission	

2. LIST OF ABBREVIATIONS

A&E	Accident and Emergency
BI	Boehringer Ingelheim
BMI	Body mass index
BTS	British Thoracic Society
CI	Confidence Interval
COPD	Chronic Obstructive Pulmonary Disease
CPRD	Clinical Practice Research Database
ENCePP	European Network of Centres for Pharmacoepidemiology and Pharmacovigilance
GP	General practitioner
GPP	Guideline for Good Pharmacoepidemiology Practices
HES	Hospital Episode Statistics
HES-APC	Hospital Episode Statistics Admitted Patient Care
HES A&E	Hospital Episode Statistics Accident and Emergency
ICS	Inhaled corticosteroids
IQR	Interquartile range
ISAC	Independent Scientific Advisory Committee
LABA	Long-acting beta agonists
LAMA	Long-acting muscarinic antagonists
LTRA	Leukotriene receptor antagonist
NIS	Non-interventional study
NISed	Non-interventional study based on existing data
OCS	oral corticosteroids
PSD	Program specification document
RCP	Royal College of Physicians
RMP	Risk management plan
SIGN	Scottish Intercollegiate Guidelines Network
UTS	Up-to-standard

3. RESPONSIBLE PARTIES

The study investigators (Global Epidemiology) at Boehringer Ingelheim International GmbH (BI) are responsible for the design and conduct of the study. The study protocol has been written following the Code of Conduct by the European Network of Centres for Pharmacoepidemiology and Pharmacovigilance (ENCePP) [[R15-4870](#)]. The investigators are responsible for conducting the study in a manner that meets regulatory standards. The study shall be conducted as described in the approved protocol. All revisions to the protocol will be properly documented as protocol amendments.

Protocol for non-interventional studies based on existing data

BI Study Number 0205-0537

c25002535-01

Proprietary confidential information © 2018 Boehringer Ingelheim International GmbH or one or more of its affiliated companies

4. ABSTRACT

Name of company: Boehringer Ingelheim			
Name of finished medicinal product: Spiriva® Respimat®			
Name of active ingredient: Tiotropium bromide (ATC code R03B B04)			
Protocol date: 3 Aug, 2018	Study number: 0205-0537	Version/Revision: 1.0	Version/Revision date: 3 Aug, 2018
Title of study:	Characteristics of patients initiating Spiriva Respimat in Asthma in the UK: a cross-sectional, non-interventional study based on the Clinical Practice Research Datalink		
Rationale and background:	
Asthma is a respiratory condition that causes symptoms of wheezing, shortness of breath, chest tightness and cough. [P18-03927] According to treatment guidelines, asthma patients at treatment step 3 and above treated with inhaled corticosteroids, often in combination with long-acting beta agonists. However, many patients continue to have symptoms despite the use of these agents. [P10-08936]
 
In late 2014, Spiriva Respimat (tiotropium bromide), a long acting anticholinergic, was approved for treatment of asthma in the UK. Since this time, it has been approved for use in asthma patients in other countries including Japan and the United States. The current BTS/SIGN Guideline for the management of asthma recommends tiotropium by soft-mist inhaler as an alternate controller therapy at steps three, four and five of the asthma treatment paradigm, on top of inhaled corticosteroid (ICS)/LABA. [P18-03927]
 
As tiotropium is the first of its class approved for the use in the treatment of asthma, it is important to identify patient clinical and socio-demographic characteristics of those who initiate this treatment as opposed to other available treatments. This type of study will allow us to evaluate potential channeling of prescribing to different patient populations.
		
Research question and objectives:	
The main objective of the study is to describe the clinical and socio-demographic characteristics of asthma patients prior to the initiation of Spiriva Respimat for the treatment of Asthma within a general clinical population using the Clinical Practice Research Database (CPRD).
 
A secondary objective will be to describe and compare the characteristics of asthma patients who initiated Spiriva Respimat to asthma patients who initiated a higher dose of ICS/LABA FDC, or leukotriene receptor antagonist (LTRA), or alternatively those who switched from the previous ICS/LABA FDC to a new ICS/LABA FDC.
		
Study design:	A cross-sectional assessment of asthma patients who initiated Spiriva Respimat, who initiated leukotriene receptor antagonist (LTRA), who received a higher dose of ICS/LABA FDC, or who switched to a new ICS/LABA FDC in asthma in the UK		

Protocol for non-interventional studies based on existing data

BI Study Number 0205-0537

c25002535-01

Proprietary confidential information © 2018 Boehringer Ingelheim International GmbH or one or more of its affiliated companies

Name of company: Boehringer Ingelheim			
Name of finished medicinal product: Spiriva® Respimat®			
Name of active ingredient: Tiotropium bromide (ATC code R03B B04)			
Protocol date: 3 Aug, 2018	Study number: 0205-0537	Version/Revision: 1.0	Version/Revision date: 3 Aug, 2018
during the study period (September, 2014-December 31, 2017). (Non-interventional study based on existing data, NISed)			
Population:	
All adult patients who had a diagnosis of asthma before the index date, who received ICS/LABA FDC treatment and who were new initiators of Spiriva Respimat or those who initiated a higher dose of ICS/LABA FDC, a LTRA, or alternatively, those switched to a new ICS/LABA FDC.
 
The index date will be defined as the date of new initiation of Spiriva Respimat or the date of initiation of, or switch to, the treatments specified above.
 
Patients with a diagnosis of COPD as well as patients on any LAMA prior to the index date will be excluded from the main analysis.
 
A history in the database of at least 1 year of continuous up-to-standard (UTS) registration in the CPRD prior to index date will be required to determine indications of use and previous treatments.
		
Variables:	
As stated above the patients will be grouped by type of treatment initiated or switched to. This will include Spiriva Respimat, a higher dose of ICS/LABA FDC, a new ICS/LABA FDC or an LTRA. Patient characteristics will be identified based on data recorded on the index date (date of dispensing/initiation of the exposure), or when a characteristic was not recorded on the index date, during the pre-index period (the one closest to the index date), unless otherwise specified.
 
The outcome is whether a patient has a cardiac arrhythmias diagnosis on the index date or in the year prior to the index date. The secondary outcome is whether a patient has a cardiac failure diagnosis on the index date or in the year prior to the index date.
 
In addition, the following covariates will be assessed in this study:
 
 • Demographic characteristics • Lifestyle factors • Asthma history and lab tests • Comorbidities • Concomitant prescriptions (both asthma related and non-asthma related prescriptions) 		
Data sources:	United Kingdom's Clinical Practice Research Datalink (CPRD) GOLD database		

Protocol for non-interventional studies based on existing data

BI Study Number 0205-0537

c25002535-01

Proprietary confidential information © 2018 Boehringer Ingelheim International GmbH or one or more of its affiliated companies

Name of company: Boehringer Ingelheim																																								
Name of finished medicinal product: Spiriva® Respimat®																																								
Name of active ingredient: Tiotropium bromide (ATC code R03B B04)																																								
Protocol date: 3 Aug, 2018	Study number: 0205-0537	Version/Revision: 1.0	Version/Revision date: 3 Aug, 2018																																					
Study size:	
The study size is dependent on the uptake of Spiriva Respimat for asthma in the CPRD. Table 1 provides a range of estimates for different prevalence estimates of disease (or characteristics). The numerator represents the number of patients with the comorbidity of interest and the denominator represents the number of new users in the population. With 500 patients we would have adequate confidence intervals around these estimates.
 
Table 1. Precision of estimates for proportion measures
 
  
 Number of New Users	95% Confidence Intervals for Various Prevalences of Diseases (%)	
 
 1%	2%	5%	7%	10%	
   
 500	0.4-2.3	1.1-3.6	3.4-7.3	5.1-9.6	7.7-12.9	
 
 800	0.5-2.0	1.2-3.2	3.7-6.7	5.4-9.0	8.1-12.3	
 
 2,000	0.6-1.5	1.5-2.7	4.1-6.0	6.0-8.2	8.8-11.3	
 
 5,000	0.8-1.3	1.6-2.4	4.4-5.6	6.3-7.7	9.2-10.9	
  
 
A feasibility check was conducted to assess the number of patients in the tiotropium group, after application of the study inclusion and exclusion criteria. The result indicated that between September 2014 and December 2017, the number of patients in the tiotropium group was around 935, which is sufficient for the study aims, as per the described precision estimates.
					Number of New Users	95% Confidence Intervals for Various Prevalences of Diseases (%)					1%	2%	5%	7%	10%	500	0.4-2.3	1.1-3.6	3.4-7.3	5.1-9.6	7.7-12.9	800	0.5-2.0	1.2-3.2	3.7-6.7	5.4-9.0	8.1-12.3	2,000	0.6-1.5	1.5-2.7	4.1-6.0	6.0-8.2	8.8-11.3	5,000	0.8-1.3	1.6-2.4	4.4-5.6	6.3-7.7	9.2-10.9
Number of New Users	95% Confidence Intervals for Various Prevalences of Diseases (%)																																							
	1%	2%	5%	7%	10%																																			
500	0.4-2.3	1.1-3.6	3.4-7.3	5.1-9.6	7.7-12.9																																			
800	0.5-2.0	1.2-3.2	3.7-6.7	5.4-9.0	8.1-12.3																																			
2,000	0.6-1.5	1.5-2.7	4.1-6.0	6.0-8.2	8.8-11.3																																			
5,000	0.8-1.3	1.6-2.4	4.4-5.6	6.3-7.7	9.2-10.9																																			
Data analysis:	
For the primary objective of the study, patient characteristics will be tabulated and summarized for all new users of Spiriva Respimat.
 
For the secondary objectives patient characteristics will be tabulated for the patients that initiated or switched to the other available treatments. Patient characteristics will be compared among patients who initiated Spiriva Respimat and patients in other treatment groups. Analyses will be conducted in unmatched cohorts and differences between Spiriva Restinmat and each of the other exposure groups will be assessed using absolute standardized differences (ASD), where an ASD of at least 10% will be considered a meaningful difference [R16-1227].
																																							
Milestones:	
Start of data collection: September 1, 2018
 
End of data collection: September 30, 2018
 
Final report of study results: December 31, 2018
																																							

5. AMENDMENTS AND UPDATES

None.

6. MILESTONES

Milestone	Planned Date
Start of data collection	September 1, 2018
End of data collection	September 30, 2018
Final report of study results:	December 31, 2018

7. RATIONALE AND BACKGROUND

Asthma is a respiratory condition that causes symptoms of wheezing, shortness of breath, chest tightness and cough [[P18-03927](#)]. According to treatment guidelines, asthma patients at treatment step 3 and above should be treated with inhaled corticosteroids often in combination with long-acting beta agonists. However, many patients continue to have symptoms despite the use of these agents [[P10-08936](#)].

In late 2014, Spiriva Respimat (tiotropium), a long acting anticholinergic, was approved for treatment of asthma in the UK. Since this time, it has been approved for use in asthma patients in other countries including Japan and the United States. In the U.K., Spiriva® Respimat® is indicated as an add-on maintenance bronchodilator treatment in adult patients with asthma who are currently treated with the maintenance combination of inhaled corticosteroids ($\geq 800\mu\text{g}$ budesonide/day or equivalent) and long-acting beta2-agonists and who experienced one or more severe exacerbations in the previous year.

The current BTS/SIGN Guideline for the management of asthma recommends tiotropium by soft-mist inhaler as an alternate controller therapy at steps three, four and five of the asthma treatment paradigm, on top of inhaled corticosteroid (ICS)/LABA [[P18-03927](#)]. Alternatively, these patients could also be treated with a higher dose of ICS or ICS/LABA or MART, addition of leukotriene receptor antagonist (LTRA), addition of theophylline, beta agonist tablet, or switching to a different ICS/LABA, as shown in [figure 1](#).

Protocol for non-interventional studies based on existing data

BI Study Number 0205-0537

c25002535-01

Proprietary confidential information © 2018 Boehringer Ingelheim International GmbH or one or more of its affiliated companies

[figure not shown]

Figure 1 Summary of asthma management in adults.

Tiotropium is the first of its class approved for the use in the treatment of asthma. After a drug is launched in the market, it is important to identify patient clinical and socio-demographic characteristics of patients who initiate this treatment as opposed to other available treatments for patients at the same stage of disease. This type of study will allow us to evaluate potential channeling of prescribing to different patient populations. The results of the current study can also be used to determine the variables included in the calculation of propensity scores in future studies.

8. RESEARCH QUESTION AND OBJECTIVES

The primary objective of the study is to describe the clinical and socio-demographic characteristics of asthma patients at the time of the initial prescription of Spiriva Respimat for the treatment of Asthma within a general clinical population using the GOLD database within Clinical Practice Research Datalink (CPRD).

A secondary objective will be to describe and compare the characteristics of asthma patients who initiated Spiriva Respimat to asthma patients who initiated a higher dose of ICS/LABA FDC, or LTRA, or alternatively those who switched to a new ICS/LABA FDC.

Protocol for non-interventional studies based on existing data

BI Study Number 0205-0537

[figure not shown]
c25002535-01

 Proprietary confidential information © 2018 Boehringer Ingelheim International GmbH or one or more of its affiliated companies

9. RESEARCH METHODS

9.1 STUDY DESIGN

This study is a cross-sectional, non-interventional study based on existing data (NISed). The UK CPRD data will be used to assess the characteristics of asthma patients who were prescribed ICS/LABA FDC before the index date and who initiated Spiriva Respimat, or received a higher dose of ICS/LABA FDC, or initiated LTRA, or switched to a new ICS/LABA FDC in the UK during the study period (September 2014-December 2017). This will allow us to assess potential channeling of prescribing to different patient populations.

Note: Study period: September 2014-December 2017.

This is a cross-sectional study and patients will not be followed up after the index date.

Patient characteristics will be evaluated on the index date, or when a characteristic was not recorded on the index date, during the pre-index period (the one closest to the index date).

In the UK, nearly all residents are registered in a general medical practice that uses electronic medical records. Some of those records are available for research purposes in the CPRD. CPRD contains diagnostic and prescribing information recorded by general practitioners (GPs) as part of their routine clinical practice in the UK. The database currently contains data for over 13.2 million patients with research-quality data from 680 UK practices; 5.69 million of these patients are active (still registered with a contributing GP practice) [[R14-5257](#)]. Patients registered are representative of the whole UK population in terms of age and sex. More detailed description of the CPRD data is provided in [section 9.4](#).

9.2 SETTING

The study population will be asthmatic patients who were prescribed ICS/LABA FDC before the index date and who initiated Spiriva Respimat, or received a higher dose of ICS/LABA FDC, or initiated LTRA, or switched to a new ICS/LABA FDC from the previous ICS/LABA FDC in the UK during the study period (September, 2014-December 31, 2017). Selection of the above therapies is based on the BTS/SIGN guideline (see [figure 1](#) in [section 7](#)). These therapies are all options at adult asthma treatment steps 3 or 4. Although theophylline and

Protocol for non-interventional studies based on existing data**BI Study Number 0205-0537****c25002535-01**

Proprietary confidential information © 2018 Boehringer Ingelheim International GmbH or one or more of its affiliated companies

beta-agonist tablet are also options for add-on therapy at steps 3 and 4, we will not include these two in the current study because they are not widely used in the U.K.

The index prescription will be one of the follows:

- The first prescription of Spiriva Respimat during the study period;
- The first prescription of ICS/LABA FDC with a higher daily dose (any higher dose) (compared to the last prescription) during the study period (if there are more than 1 dose increase during the study period, only the first dose increase will be used in the analyses);
- The first prescription of LTRA during the study period;
- The first prescription of a new ICS/LABA FDC during the study period.

The index date is defined as the date of the index prescription.

In this study, all patients will be required to have at least 1 year of continuous up-to-standard (UTS) registration in the CPRD prior to index date to determine indications of use and previous treatments.

The in- and exclusion criteria of this study are as follows:

Inclusion criteria:

- Aged 18 years and above at the index date
- At least 12 months of continuous registration prior to the index date in a practice contributing up to standard (UTS) data to the CPRD
- Had a diagnosis of asthma before the index date (In this study, an asthma diagnosis is defined as at least one medcode for asthma prior to the index date. Please refer to [annex 3](#) for the detailed medcodes for asthma and the related Read terms)
- Being treated with ICS/LABA FDC before the index date (at least one prescription within 3 months before the index date)
- Patients who were new users of Spiriva Respimat, or LTRA, or patients who were prescribed a higher dose of ICS/LABA FDC, or patients who switched to a new ICS/LABA FDC from the previous ICS/LABA FDC

Exclusion criteria:

- Patients who were prescribed other LAMA any time before or on the index date
- In the primary analysis, patients who were diagnosed with COPD before or on the index date will be excluded from the study.

(In this study, a COPD diagnosis is defined as at least one Readcode for COPD before or on the index date. Please refer to [annex 4](#) for the detailed medcodes for COPD and the related readterms)

Protocol for non-interventional studies based on existing data

BI Study Number 0205-0537

c25002535-01

 Proprietary confidential information © 2018 Boehringer Ingelheim International GmbH or one or more of its affiliated companies

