9.3.1 Exposures

The study drug of interest is Spiriva Respimat. The exposure in the Spiriva group will be initiation of Spiriva Respimat. The exposure in the comparator group will include: 1) initiation of LTRA; 2) an increase in daily dose of ICS/LABA FDC; and 3) switching to a new ICS/LABA FDC.

To make sure that patients who initiated Spiriva Respimat or LTRA are new users of these drugs, patients who initiated Spiriva Respimat must have no exposure to tiotropium before the index date, and patients who initiated LTRA must have no exposure to LTRA before the index date.

An increase in daily dose of ICS/LABA FDC refers to any increase in the daily dose. If there was more than 1 dose increase during the study period, only the first dose increase will be included in the analysis.

Switching to a new ICS/LABA FDC refers to patients who switched to a new ICS/LABA FDC with different drug ingredient that was not prescribed during the pre-index period. If there was more than 1 switch during the study period, only the first switch will be used in the analysis.

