9.5 STUDY SIZE

The study size is dependent on the uptake of Spiriva Respimat for asthma in the CPRD. [Table 1](#) provides a range of estimates for different prevalence estimates of disease (or characteristics). The numerator represents the number of patients with the comorbidity of interest and the denominator represents the number of new users in the population. With 500 patients we would have adequate confidence intervals around these estimates.

Table 1 Precision of estimates for proportion measures

Number of New Users	95% Confidence Intervals for Various Prevalences of Diseases (%)				
	1%	2%	5%	7%	10%
500	0.4-2.3	1.1-3.6	3.4-7.3	5.1-9.6	7.7-12.9
800	0.5-2.0	1.2-3.2	3.7-6.7	5.4-9.0	8.1-12.3
2,000	0.6-1.5	1.5-2.7	4.1-6.0	6.0-8.2	8.8-11.3
5,000	0.8-1.3	1.6-2.4	4.4-5.6	6.3-7.7	9.2-10.9

A feasibility check was conducted to assess the number of patients in the tiotropium group, after application of the study inclusion and exclusion criteria. The result indicated that between September 2014 and December 2017, the number of patients in the tiotropium group was 935.

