9.7.1 Main analysis

The primary objective of this study is to describe the clinical and socio-demographic characteristics of asthma patients prior to the initiation of Spiriva Respimat for the treatment of Asthma. For this objective, patient baseline characteristics (as described in the “outcomes” and “covariates” section) will be tabulated and summarized for all new users of Spiriva Respimat. Means, standard deviations, medians, minimum, maximum, and interquartile range

(IQR) will be used to present continuous variables, counts and percentages will be used to present categorical variables.

The secondary objective of this study is to describe and compare the characteristics of asthma patients who initiated Spiriva Respimat to asthma patients who initiated a higher dose of ICS/LABA FDC, or LTRA, or alternatively those who switched from the previous ICS/LABA FDC to a new ICS/LABA FDC. For this objective, patient characteristics (as described in the “outcomes” and “covariates” section) will be tabulated for the patients that initiated or switched to the other available treatments separately, using measures as described for the patient baseline characteristics of Spiriva.

Patient characteristics (as described in the “outcomes” and “covariates” section) will be compared among patients who initiated Spiriva Respimat and patients in other treatment groups. Analyses will be conducted in unmatched cohorts and differences between spiriva restinmat and each of the other exposure groups will be assessed using absolute standardized differences (ASD), where an ASD of at least 10% will be considered a meaningful difference [[R16-1227](#)].

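### The secondary comparison uses crude ASDs over a window that opens at launch and never looks at index year, so calendar trend and channeling cannot be told apart

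*Protocol*

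**What the plan says.** **Index dates (Protocol 9.2 and 9.3.1).** The study period runs from September 2014 to 31 December 2017. All four groups are indexed on a first qualifying prescription within it. For Spiriva this is "The first prescription of Spiriva Respimat during the study period". For dose increases, any higher daily dose than the last prescription counts, and "only the first dose increase will be used in the analyses"; no period free of earlier increases is required. For switches, "only the first switch will be used in the analysis", and the new ingredient must not have been prescribed in the pre-index period. LTRA differs again: "patients who initiated LTRA must have no exposure to LTRA before the index date".

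**Launch (Protocol 7 and 9.5).** "In late 2014, Spiriva Respimat (tiotropium), a long acting anticholinergic, was approved for treatment of asthma in the UK". On numbers, "The study size is dependent on the uptake of Spiriva Respimat for asthma in the CPRD". The feasibility count is 935 for the whole period, with no breakdown by year.

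**Comparison (Protocol 9.7.1).** "Analyses will be conducted in unmatched cohorts", and an ASD of 10% or more counts as meaningful. Sections 7 and 9.1 give the purpose as assessing potential channeling.

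**Calendar time.** Index year is absent from the covariate list in 9.3.3 and from the analysis in 9.7.1. Section 9.9 does not mention secular trend, and 9.12 declares no bias.

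**The concern.** If Spiriva starts sit later in the window than comparator index dates, anything that changed between 2014 and 2017 appears as a difference between treatments. The protocol offers three routes:

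- **Recording.** Section 9.9 warns that smoking, BMI and eosinophil count may be poorly recorded, and 9.7.3 shows missing values as a category of their own. A change in recording over time would enter the ASDs directly.
- **Look-back.** Section 9.9 says comorbidity will use all data before the index date. For patients registered at similar times, a later index date means a longer look-back and more recorded comorbidity. The two cardiac outcomes have a fixed one-year window and escape this route.
- **Practice.** The guideline cited for treatment steps is dated September 2016, inside the window.

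At stake is the secondary comparison and its later use: section 7 says the results may guide the choice of propensity-score variables in future studies. A calendar-driven difference could be carried forward while index year itself is never considered. The description of Spiriva starters, the primary objective, does not depend on any of this.

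**Working it through.** **The plan's own figure.** The only calculated figure is Table 1, the within-group precision of a proportion. The Wilson interval reproduces 19 of its 20 cells; the other (n = 2,000, 10%) computes to 8.76-11.39 against the printed 8.8-11.3. It does not bear on this point. The protocol has no figure for index timing, so the rates, uptake shapes and drifts below are assumptions.

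**1. Comparator timing.** The window is T = 40 months = 3.33 years. With no front-loading the mean index time is T/2 = 1.67 y. If the first in-period event occurs at constant rate h, the mean is 1/h - T·e^(-hT)/(1 - e^(-hT)).

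| h per year | mean (y) | shift from 1.67 (y) |
|---|---|---|
| 0.1 | 1.57 | 0.09 |
| 0.2 | 1.48 | 0.18 |
| 0.3 | 1.39 | 0.27 |

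The first-in-period rule thus moves the mean by about 0.1 to 0.3 y. The model fits dose increases best. Switches are restricted by the new-ingredient condition, and patients entering the database during the period weaken the shift for both. A first-ever LTRA start is not reset by the opening of the window, so 1.67 y is kept for that group.

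**2. Spiriva timing.** Three start densities growing from zero at the opening:

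- saturating, proportional to 1 - e^(-t): mean 1.99 y
- linear: 2T/3 = 2.22 y
- quadratic: 3T/4 = 2.50 y

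Against 1.67 y, uptake alone gives 0.32, 0.56 and 0.83 y. This is the whole gap for LTRA.

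**3. Combined gap, dose-increase and switch groups.**

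| h | saturating | linear | quadratic |
|---|---|---|---|
| 0.1 | 0.41 y | 0.65 y | 0.93 y |
| 0.3 | 0.59 y | 0.83 y | 1.11 y |

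Expressed as an ASD on index date itself, this is about 0.46 to 1.37. For example, with h = 0.1 and linear uptake the variances are 0.921 and 0.617, the pooled SD is √((0.921 + 0.617)/2) = 0.88, and 0.65/0.88 = 0.74.

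**4. ASD produced by trend alone** = gap × drift in SD per year.

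- Drift needed for 0.10: 0.10/1.11 = 0.09 at the widest gap, 0.10/0.65 = 0.15 at the linear case, 0.10/0.41 = 0.24 at the narrowest. Roughly 0.1 to 0.2 SD per year.
- For a characteristic with 20% prevalence (SD 0.40), gaps of 0.9 and 0.55 y require 0.111 × 40 = 4.4 and 0.182 × 40 = 7.3 percentage points per year.
- A drift of 0.05 SD per year at a gap of 0.65 y gives 0.03. That moves a true ASD of 0.07 to 0.10, or a true 0.12 to 0.09, depending on direction.

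**5. Effective size after weighting to Spiriva's index years.** The retained fraction is 1/Σ(s²/c), where s and c are the Spiriva and comparator shares in 2014 (four months), 2015, 2016 and 2017. With h = 0.1 and linear uptake, s = 0.01, 0.15, 0.33, 0.51 and c = 0.116, 0.325, 0.294, 0.266. The sum is 0.001 + 0.069 + 0.370 + 0.978 = 1.418, so 71% is retained. By the same formula it is 85% with h = 0.1 and saturating uptake, and 41% with h = 0.3 and quadratic uptake.

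**The case against.** The case against is substantial:

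- **The first-event rule is ordinary.** It keeps one index event per patient in a group, and Spiriva is indexed on a first prescription too. A reader might infer that the rule is the main cause and front-loads all comparators. The documents do not support that: LTRA starters must never have had an LTRA, switches are restricted, and in the linear case with h = 0.1, 0.56 of the 0.65 y gap comes from uptake. This objection stands.
- **The inputs are assumed.** The uptake sentence in 9.5 concerns total study size, not the shape of uptake over time. No passage supports drift strong enough to cross 10% unaided. This also stands.
- **The study is descriptive.** Section 9.7.1 calls an ASD of 10% meaningful; it does not equate it with channeling, and sections 7 and 9.1 speak only of potential channeling. That is a fair correction to a harsher reading. Yet with index year unseen, the comparison cannot distinguish the two explanations.
- **An analysis plan could add an index-year table.** It could, and absence of that detail alone would not be a finding. But the protocol itself fixes the covariate list and the unmatched comparison, omits secular trend from 9.9 and declares no bias in 9.12.

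**Conclusion.** The point holds as a minor design weakness of the secondary comparison. What rests on the text is that the window opens at about the asthma approval, the ASDs are crude, and calendar time appears in neither the covariates, the analysis nor the limitations. What rests on assumption is the size: gaps in mean index date of about 0.4 to 1.1 y for the dose-increase and switch groups, and 0.3 to 0.8 y for LTRA, driven mostly by uptake.

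A reader might infer that calendar trend will by itself produce ASDs above 10%. The documents do not show that; it would take drift of roughly 0.1 to 0.2 SD per year. The supportable conclusion is narrower: the groups may differ considerably in index date, no listed table would show it, and modest drift could tip results near the cut-off either way.

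**What to change.** 1. In 9.3.3, add calendar year of index date and tabulate it by treatment group.
2. In 9.7.1, beside the crude ASDs, report ASDs with each comparator group weighted to the Spiriva index-year distribution. The crude comparison stays as planned; a marked change between columns points to calendar time.
3. In 9.9 and 9.12, name secular trend and differing index dates as a limitation.

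The index date is already in the data, so the cost is one covariate, one column and some effective comparator size. The loss is slight if index dates nearly align and larger if they do not (about 85% retained in the mildest combined case above, 41% in the most extreme). Because 2014 contributes only four months and possibly few Spiriva starts, it may need to be merged with 2015.
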